Patients will be recruited from both the Johns Hopkins Department of Dermatology and Thoracic Surgery. The recruitment of these patients will occur during normal appointments and clinic visits at Johns Hopkins Hospital. Physicians in either department seeing hyperhidrosis cases will inform patients about the existence of the study. The International Hyperhidrosis Society reserves the right to notify persons regarding the existence of the research being conducted which would amount to no more than a link to the above website. Recruitment will not involve any media advertisements or flyers. The trial will be listed on clinicaltirals.gov and a link will provided to the Hopkins Center for Sweat Disorders website (http://www.hopkinsmedicine.org/sweat_disorders/).

Patients will be asked to complete the Hyperhidrosis Disease Severity Scale (HDSS) as a prescreening survey. The HDSS (below) is a diagnostic tool that qualitatively measures (Likert scaled 1-4) disease-specific severity of the patient's condition based on the degree to which daily activities are impacted:¹⁶

Hyperhidrosis Disease Severity Scale:

"How would you rate the severity of your hyperhidrosis?"

- 1. My sweating is never noticeable and never interferes with my daily activities
- 2. My sweating is tolerable but sometimes interferes with my daily activities
- 3. My sweating is barely tolerable and frequently interferes with my daily activities
- 4. My sweating is intolerable and always interferes with my daily activities

A score of 1 or 2 indicates mild or moderate hyperhidrosis while a score of 3 or 4 indicates severe hyperhidrosis. Patients scoring 3 or 4 on the HDSS who also meet the additional inclusion/exclusion criteria will be offered enrollment in the study. The HDSS has been validated for reliability by analysis in three studies and with correlative comparison to the Hyperhidrosis Impact Questionnaire (HHIQ), Dermatology Quality of Life Index (DLQI), and gravimetric sweat production measurements.¹⁶

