These potential participants will be approached directly following their clinical visits. For patients who then agree to participate in the study, written informed consent will be obtained. During the consenting process, the study will be thoroughly explained along with a description of the miraDry ® system and the predicted benefits and possible risks therein. No post-consent screening will be performed. No pre-consent Protected Health Information will be reviewed prior to the signing of consent.

Each participant will schedule an appointment with behavioral medicine and asked to complete additional, survey evaluations (all of which have been independently validated) as listed below. The same slate of surveys will be given at the second appointment and at follow-up.

Domain	Survey	Applicable Ages
Dermatology QOL	DLQI	>17 years
Broadband psychopathology	BASC	17-21 years
	BASC (college)	18-25 years
Anxiety	Zung Anxiety Self	>17 years
Depression	BDI-2	>17 years

Each participant will also schedule two miraDry ® treatment appointments approximatelythree months apart. The administration of miraDry ® treatments will take place at Greenspring located at [name].

At each of these treatment appointments, each participant will be asked to complete the above surveys reflecting their current states.

The miraDry ® treatment will be administered using a standard treatment procedure as follows:

- MiraDry system powered on and goes through a self check
- Patient positions self supine on exam table with bilateral axilla exposed by patient placing arms behind head
- Right & left axilla hair bearing area measured and appropriate water tatoo applied to axilla using isopropyl alcohol
- Hibiclens applied to right and left axilla and 1 percent lidocaine with epinephrine 1:100,000 injected at sites indicted by water tattoo
- Sterile KY jelly applied to right and left axilla
- New sterile biotip package opened and connected to MiraDry machine
- Procedure initiated using energy level 3-5, with the number of treatment sites dependent on the size of the hair baring area
- 2 reusable ice packs wrapped in paper towels given to patient to apply to axilla bilaterally

Additionally, study patients will be given the following post-procedure instructions:

- Continue ice packs for the next few days & to always wrap ice pack in a towel to prevent frost bite

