- Keep underarms clean using liquid soap to clean the underarms twice a day until the underarm is healed from procedure
- Do not shave underarm until underarm tenderness is resolved and any wounds are healed
- Do not apply antiperspirant or deodorant until underarm tenderness is resoled and any wounds are healed
- Wear loose clothing for 5-7 days to prevent any underarm irritation
- Apply an over the counter antibiotic ointment twice daily to the underarms for 1 week
- An anti-inflammatory over-the-counter drug such as ibuprofen can help manage pain and reduce swelling. It should be taken according to package instructions and as long as there are no contraindications to patient taking this medication.

b. Study duration and number of study visits required of research participants.

This study should take approximately 2 years to complete. Participants will be required to be present for at least 4 study visits. The first visit will be for consultation and to determine whether the patient meets the inclusion/exclusion criteria. Then each consented patient will schedule a behavioral medicine appointment for initial psychometric evaluation. This is followed by 2 visits to administer the miraDry ® treatment, spaced approximately 3 months apart. A follow up survey will take place roughly between 6 months and 1 year after the first treatment visit. The follow up visit is optional because the survey will be administered over phone, through the mail, or electronically if the patient is unavailable for study visit.

c. Blinding, including justification for blinding or not blinding the trial, if applicable.

This study will compare patient psychometric data at the time of before treatment/consultation to corresponding post-treatment information. Researchers will therefore be blinded to a patient's pre-treatment information when collecting post-treatment data via telephone call or in any situation involving direct patient interaction to eliminate potential bias when soliciting, recording, or analyzing study data.

d. Justification of why participants will not receive routine care or will have current therapy stopped.

N/A

e. Justification for inclusion of a placebo or non-treatment group.

N/A

f. Definition of treatment failure or participant removal criteria.

N/A

g. Description of what happens to participants receiving therapy when study ends or if a participant's participation in the study ends prematurely.

N/A

5. Inclusion/Exclusion Criteria

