Lidocaine with epinephrine will be used as a local anesthetic to the treatment site. Additionally, hibliclens with chlorhexidine 4% is an antiseptic antibacterial agent routinely used to prevent the growth of bacteria on the skin and will be used at the treatment site. The drugs used in the study will be the same drug provided for the entire Johns Hopkins Department of Dermatology. There will not be a separate batch of this drug for the sole purposes of this study as this study is not a clinical trial and use of the drug is unlikely to interfere with study results.

b. Justification and safety information if FDA approved drugs will be administered for non-FDA approved indications or if doses or routes of administration or participant populations are changed.

N/A

c. Justification and safety information if non-FDA approved drugs without an IND will be administered.

N/A

7. Study Statistics

a. Primary outcome variable.

Pre- and post-treatment scores on the HHDS and other surveys described in Section 4a.

b. Secondary outcome variables.

Same as primary outcome variable. To compare miraDry ® treatment to surgical intervention, the data collected from the above surveys will be compared to previously collected pre- and post-operative survey data given to surgical patients.

c. Statistical plan including sample size justification and interim data analysis.

The cohort of axillary hyperhidrosis patients will be constituted by roughly 24 eligible individuals who meet the inclusion/exclusion criteria described in Section 5. This sample size was so determined based on the number of funded complete miraDry ® treatments. However, power analyses of existing clinical data would suggest 80% power to detect statistically significant decreases in anxiety and depressive symptoms with our proposed sample size. Data will be analyzed as it is collected for each study visit stage and again after follow-up for pre- vs. post- treatment comparison.

d. Early stopping rules.

Each patient has the right to discontinue their participation in the study at any time. All patients who wish to terminate participation in the study will have their request fulfilled effective immediately and indefinitely.

A participant may have their participation in the study discontinued if problems arise during the course of their involvement which require deviations from the approved protocol (section 8c).

8. Risks

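### The primary outcome needs pre- and post-treatment HDSS scores, but the HDSS is named only as the entry screen and is missing from the table of repeated surveys

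*Combined protocol and SAP*

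**What the plan says.** Section 7a gives the primary outcome as "Pre- and post-treatment scores on the HHDS and other surveys described in Section 4a". The abbreviation HHDS appears nowhere else in the document.

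Section 4a introduces the HDSS for screening: "Patients will be asked to complete the Hyperhidrosis Disease Severity Scale (HDSS) as a prescreening survey". Patients who score 3 or 4 may enrol, and Section 5 repeats that threshold. After consent, participants are "asked to complete additional, survey evaluations (all of which have been independently validated) as listed below". The table that follows lists the DLQI, two BASC forms, the Zung anxiety scale and the BDI-2. The repeat schedule reads "The same slate of surveys will be given at the second appointment and at follow-up". For the two treatment visits the text adds: "At each of these treatment appointments, each participant will be asked to complete the above surveys reflecting their current states".

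On visit order, Section 4b says "The first visit will be for consultation and to determine whether the patient meets the inclusion/exclusion criteria" and continues "Then each consented patient will schedule a behavioral medicine appointment for initial psychometric evaluation". Section 10a also places baseline data collection at the behavioral medicine visit. Section 4c describes the comparison in these terms: "This study will compare patient psychometric data at the time of before treatment/consultation to corresponding post-treatment information".

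**The concern.** The outcome definition and the assessment schedule do not match. Section 7a calls for a post-treatment score on the one instrument it singles out, yet the schedule never names that instrument after screening. Staff working from the Section 4a table would not administer it, and a missed self-rating of current state cannot be recovered later.

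The second problem is the baseline. The only explicit pre-treatment HDSS is the qualifying score, and the plan does not say whether it may serve as the pre-treatment value. Patients chosen for a high reading tend to score lower when asked again, even if nothing has changed. With no control group (Section 4e), that fall would look like a treatment effect. This harm arises only if a post-treatment HDSS is collected and the screening score is used as its baseline.

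**Working it through.** **Text check.** The plan gives no figure to reproduce on this point, so the first step is to compare the mentions.

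- Section 4a, screening: the HDSS is named as the prescreening survey and entry threshold.
- Section 4a, table of further surveys: five entries, none of them the HDSS.
- Section 4a, second appointment and follow-up: the same slate, which refers to that table.
- Section 4a, treatment visits: the surveys above, with no instrument named.
- Section 4b, follow-up: a survey 6 months to 1 year after first treatment, with no instrument named.
- Section 5: the HDSS is named again, for eligibility only. The age criterion refers to a first HHIQ, but the HHIQ is not scheduled anywhere either.
- Section 7a: pre- and post-treatment HHDS.

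Reading HHDS as HDSS is an inference, but the best one: it is the only severity scale set out in Section 4a, and the letters nearly match. If the HHIQ were meant, the gap would be the same.

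**Possible size of the baseline problem.** The documents give no HDSS reliability, clinic score distribution or named test, so all of these are assumed. The model is observed score = stable latent trait + error, cut into four categories. Patients are selected on a screening score of 3 or more and the treatment effect is zero. Each case has 20,000 simulated trials of n = 24, and a two-sided 5% paired t-test is counted when significant in the direction of a fall (nominal 2.5%). Post-treatment error is independent. The error at a re-measured baseline has correlation ρ with the screening error.

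Results at latent ICC 0.8:

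| Assumed clinic scores 1/2/3/4 (%) | Below 3 | Mean fall, screening baseline | False falls, screening baseline | False falls, re-measured, ρ = 0 | ρ = 0.3 | ρ = 0.5 | ρ = 0.7 |
|---|---|---|---|---|---|---|---|
| 20/30/30/20 | 50% | 0.247 | 36% | 2.6% | 5.4% | 8.7% | 13.1% |
| 10/30/35/25 | 40% | 0.186 | 25% | 2.4% | 4.6% | 6.6% | 9.2% |
| 5/25/40/30 | 30% | 0.136 | 17% | 2.4% | 3.7% | 5.1% | 7.0% |
| 5/15/40/40 | 20% | 0.100 | 11% | 2.2% | 3.1% | 4.4% | 5.6% |
| 2/8/45/45 | 10% | 0.053 | 6% | 2.3% | 2.8% | 3.3% | 3.8% |
| 1/4/55/40 | 5% | 0.029 | 4% | 2.3% | 2.5% | 2.7% | 3.1% |

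To read the first row: the mean screening score among those selected is (30 × 3 + 20 × 4) / 50 = 3.40. With no effect, the later mean is 3.40 − 0.247 = 3.153.

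At ρ = 0.5 the mean fall from a re-measured baseline is 0.096 in the first row and 0.045 in the third. The share of the apparent fall removed is 1 − 0.096/0.247 = 61% and 1 − 0.045/0.136 = 67%. The other rows lie between these.

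Over ICC 0.6 to 0.9, the false-fall rate is about 3% to 62% with the screening baseline. With a re-measured baseline and ρ from 0.3 to 0.7 it is about 2.5% to 24%.

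**The case against.** The strongest reply is that the schedule is ambiguous rather than empty. Section 7a treats the scale as one of the Section 4a surveys, Section 4a calls it a survey, and the treatment-visit sentence asks for the surveys above. Read together, these could put the HDSS at both treatment visits. That reading is possible, but the nearest antecedent is the table of further surveys. It would also supply only one post-treatment point, at the second treatment visit, because follow-up is tied to the tabulated slate. It does not give a dependable score after the full course.

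The bias is also conditional. No text says the screening score is the baseline, and Section 10a points to the behavioral medicine visit. This is right, but Section 10a does not help while the HDSS is absent from the surveys given there.

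The simulated range is wide and every input is assumed. The top of the range needs half of specialist-clinic patients to score below 3 together with low reliability. This also stands, and the figures are illustrative only. The schedule gap does not depend on them.

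The loose wording in Section 4c can be reconciled: Section 4b uses the word consultation for the eligibility visit, but Section 11 uses it for the behavioral medicine visit. It is not a separate error. Finally, the primary objective is psychosocial functioning, so removing the HDSS from the primary outcome would also resolve the conflict. That is a legitimate alternative, and it does not make the proposed change unsound.

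**Conclusion.** The concern holds. Section 7a and the Section 4a schedule conflict. Followed as written, the plan does not assure a post-treatment HDSS, and the only explicit pre-treatment value is the score used for entry. This conclusion rests on reading HHDS as HDSS and needs no calculation.

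Regression to the mean is a further risk if the screening score becomes the baseline. Its direction is clear but its size is unknown: close to nominal if few clinic patients score below 3, and substantial if many do. The consequence is limited, because the HDSS is one component of the primary outcome and the power statement in Section 7c covers only anxiety and depressive symptoms. The point should be fixed, but it does not undermine the whole design.

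**What to change.** - In Section 7a, correct HHDS to HDSS.
- In Section 4a, add the HDSS to the survey table, so that it is completed with the other surveys at the behavioral medicine visit, at both treatment visits before the procedure, and at follow-up.
- State that the screening HDSS serves eligibility only. Measure HDSS change from the post-enrolment, pre-treatment score taken at the behavioral medicine visit, and name that visit in Section 4c.
- Say in the report that some regression to the mean may remain, since patients may enrol during a bad spell that lasts to the baseline visit.

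The cost is one single-item question at each contact already planned, plus a wording amendment to Sections 4a, 4c and 7a. The downside is that the apparent HDSS improvement may be smaller. If the sponsor does not want the HDSS as an outcome, removing it from Section 7a would also end the inconsistency.

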Primary hyperhidrosis is a pathological condition characterized by the idiopathic and excessive secretion of sweat beyond normal physiological demand and is localized at particular foci such as the face, axilla, palms of the hands, and soles of the feet. Patients seeking medical attention for hyperhidrosis often report disruptions to their professional and/or social lives due to sweating and subsequently experience many psychosocial difficulties, such as anxiety, social phobia, and depression. Therefore, a psychiatric explanation of causality is frequently offered for these patients during diagnosis. Excessive sweating is often mistakenly interpreted as a symptom of an anxiety disorder and can be cause for social embarrassment, exacerbating emotional stress and social avoidance. As currently constituted, the treatment of secondary psychosocial symptoms in primary hyperhidrosis is poorly understood and requires further investigation. We have previously collected data which showed substantial improvement in quality-of-life and psychometric evaluation of primary hyperhidrosis patients after surgical intervention. These data suggest the profoundly beneficial potential of medical treatments in terms of psychosocial deficits that were previously deemed primarily psychological. This study aims to evaluate the efficacy of miraDry R a novel non-invasive treatment system for primary hyperhidrosis of the axillae. This study hypothesizes a similar finding in the miraDry ® system as was observed for the surgical modality. If this prospective study finds a significant improvement in psychometric evaluation scores after miraDry ® treatment, then it would strongly suggest that patients seeking medical intervention to alleviate excessive sweating should experience marked improvement not only in their levels of sweating, but also in the psychopathological symptoms that they experienced pre-treatment. These findings could result in substantial advantage for hyperhidrosis patients in the future. It is well documented that primary hyperhidrosis can be an extremely debilitating condition so clearly a more robust understanding of the condition and effective evaluation of treatment options confers much tangible benefit for patients.

2. Objectives (include all primary and secondary objectives)

Primary Objective:

1. To evaluate the effectiveness of the miraDry ® treatment system for psychosocial functioning in patients heavily affected by axillary hyperhidrosis.

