Secondary Objectives:

- 2. To characterize the outcomes of and clinical response to the miraDry ® treatment system with respect to the aforementioned criteria.
- 3. To compare the results of non-invasive miraDry ® treatment system to the existing surgical correction with respect to the aforementioned criteria.

3. Background (briefly describe pre-clinical and clinical data, current experience with procedures, drug or device, and any other relevant information to justify the research)

Primary hyperhidrosis has been estimated to affect up to three percent of the general population, but remains a disorder of unknown etiology.¹ Excessive sweating due to hyperhidrosis has been shown to have profound effects on patients' physical and mental quality of life, with functional impairments negatively impacting work productivity, daily activities, willingness to participate in social situations, and personal relationships. In particular, patients have been shown to report being extremely limited in developing personal relationships, attending occasions with family or friends, sexual activities, meeting people, public places, and shaking hands.²

Primary hyperhidrosis may be often incorrectly assumed to be a symptom of an anxiety disorder, but anxiety is not assumed to be a secondary effect of excessive sweating.³ Not surprisingly, increased sweating is frequently seen in patients with social anxiety disorder and strongly associated with elevated levels of disability, fear, and avoidance.⁴ Studies have shown that hyperhidrosis patients self-report elevated symptoms of psychopathology. However, previous psychological studies have shown that analysis of patients suffering from hyperhidrosis does not yield any evidence of either increased incidence of mental disorders in this group or of a causal role of psychiatric disorders in this condition.^{3,5,6} The most recent clinical evidence suggests that the above relationship is consistent with a model of social anxiety simply as a mediator of sweating-related disability, not as a causal factor.⁷

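### The plan reads falling survey scores as psychological benefit beyond reduced sweating, but has no step to check whether the psychological scales contain sweat-related items

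*Combined protocol and SAP*

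**What the plan says.** The primary objective (Section 2) is to evaluate the device "for psychosocial functioning in patients heavily affected by axillary hyperhidrosis". Section 7a gives the primary outcome as "Pre- and post-treatment scores on the HHDS and other surveys described in Section 4a". The abbreviation there is apparently the Hyperhidrosis Disease Severity Scale (HDSS) of Section 4a. The other surveys in the Section 4a table are the DLQI, two BASC forms, the anxiety scale listed as "Zung Anxiety Self", and the BDI-2. No subscore, item set or item exclusion is named for any of them.

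The opening summary says how an improvement would be read: patients should get better in their sweating, "but also in the psychopathological symptoms that they experienced pre-treatment". It also warns that "Excessive sweating is often mistakenly interpreted as a symptom of an anxiety disorder", and the Background (Section 3) repeats this: "Primary hyperhidrosis may be often incorrectly assumed to be a symptom of an anxiety disorder".

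Section 7c provides for a comparison of pre-treatment with post-treatment data and describes no item-level analysis. The only survey item printed anywhere is the HDSS, whose top category is "My sweating is intolerable and always interferes with my daily activities".

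**The concern.** The intended conclusion has two parts: sweating improves, and psychological symptoms improve as well. The second part needs a measure that does not move merely because sweating moved. Every participant enters with an HDSS of 3 or 4 and receives a treatment meant to reduce sweating. If a psychological form asks about sweating or damp skin, that answer may be high at baseline because of the skin condition and lower afterwards because of the device, with no change in worry or mood. Part of the first effect would then be counted again as the second.

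Nothing else in the design would reveal this. There is no control group. The surgical comparison data come from another treatment that reduces sweating. Blinding the data collectors to pre-treatment answers does not change what a questionnaire item asks. Section 9 uses a positive result to argue that patients could be spared psychiatric medication, so the attribution matters.

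**Working it through.** **1. The plan's own figure.** Section 7c claims 80% power for decreases in anxiety and depressive symptoms, with "roughly 24 eligible individuals who meet the inclusion/exclusion criteria described in Section 5". It gives no effect size, SD of change, significance level, sidedness or test, so the claim cannot be reproduced. It can be back-solved for a paired comparison with n = 24 and an assumed two-sided 5% level:
- Normal approximation: d = (1.960 + 0.842)/√24 = 0.57.
- Noncentral t with 23 df: d = 0.60.

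The 80% is therefore possible if the true change is about 0.6 SD. That value is a yardstick for the shifts below.

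**2. What the documents fix about item overlap.**
- HDSS: the single item is a sweating rating, so the overlap is complete.
- Zung anxiety, BASC, BDI-2: the items, their number and the scoring are not given, so the overlap is unknown.

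**3. Size, if there is overlap (all inputs assumed).** Let k be the number of sweat items, p the mean fall per item in points, and s the SD of the change in total score. The shift with no psychological change is d = k × p / s. The chance of a significant decrease is the probability that a noncentral t (23 df, noncentrality d√24) exceeds 2.069. With d = 0 this is 2.5%.

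| k | p | s | d | Share of 0.597 | Chance of significant decrease |
|---|---|---|---|---|---|
| 0 | – | any | 0 | 0% | 2.5% |
| 1 | 0.5 | 8 | 0.06 | 10% | 5% |
| 1 | 1 | 8 | 0.125 | 21% | 8.5% |
| 1 | 1 | 6 | 0.17 | 28% | 12% |
| 1 | 2 | 6 | 0.33 | 56% | 35% |
| 2 | 1 | 8 | 0.25 | 42% | 22% |
| 2 | 2 | 6 | 0.67 | 112% | 88% |

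Worked row: k = 1, p = 1, s = 6 gives d = 1/6 = 0.167 and noncentrality 0.167 × √24 = 0.82, hence 12%.

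**4. Reading.** The range runs from nothing to large, and no input in it comes from the documents. The last row needs two items, each falling by a mean of 2 points across all patients, with a low assumed SD. The table shows that the question deserves a check; it does not estimate the bias.

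**The case against.** The strongest reply is that the key fact is absent. The protocol names the scales but prints none of their psychological items, so nothing shows that any of them asks about sweating. This stands, and it is why the point is conditional.

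The mechanism also has limits. The treatment acts locally on the axillae. An item about sweating elsewhere need not respond, and nothing in the protocol links the device to flushing. This stands too: an item may fall, not must, and flushing items do not belong on the list. A response remains plausible for items on sweating in general, because participants are enrolled for primarily axillary disease.

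The protocol's remarks on sweating and anxiety concern diagnosis, not questionnaire content. A reader might infer from them that the anxiety scale is known to be contaminated, or that the study is bound to repeat the misreading it sets out to correct. The documents support neither. Likewise, Section 7a says only scores; that these are full totals is the natural reading, not stated text.

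Finally, the intended conclusion covers depression and broader psychopathology, so one affected anxiety item would not produce it alone. And Section 4a relies on the surveys having been validated, which a shortened score is not. Both stand. They argue for keeping the validated total as the main score, not for leaving the items unchecked.

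**Conclusion.** The point holds in conditional form. The plan attributes a fall in scores to psychological benefit beyond reduced sweating, and has no step to find out whether the psychological scales contain items that sweat reduction could move directly. If there is no such item, the bias is zero. If there is one, its size cannot be determined from the documents; the illustrative chances of a significant decrease, from 5% to 88% against 2.5% by chance, rest wholly on assumed item counts, item changes and SDs.

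A reader might go further and conclude that a significant anxiety result would be an artefact, or that the 88% case is likely. The documents do not support that. Only for the HDSS is the overlap certain: it rates sweating, yet is apparently named first in the primary outcome of a psychosocial objective.

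**What to change.** Add to Section 7c:

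1. Before any post-treatment data are analysed, list the items on the Zung, BASC and BDI-2 forms that ask directly about sweating or damp skin. Because 7c has data analysed at each visit stage, the list must be fixed before the first post-treatment surveys are examined.
2. Keep the validated total of each scale as the main score.
3. Report a pre-specified sensitivity analysis of the pre-post change with the listed items removed and the remainder prorated, beside the full-score result, each with its confidence interval. If a form has no such item, say so; the two scores are then the same.
4. State that psychological symptoms improved beyond sweating only if the direction and approximate size of the change persist in that analysis, and define in advance what counts as persisting.
5. Do not count the HDSS as evidence of psychological benefit; report it as a sweating outcome.

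The cost is a few lines of text and analysis on responses the surveys already generate, with no new visits or patients, provided item-level answers are kept as well as totals. The reduced score is not validated. It may also not be comparable with the earlier surgical data if only totals survive there. For both reasons it serves as a sensitivity analysis and does not replace the full score.
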